Patients who are planning to schedule pelvic reconstructive surgery with Women's Center for Pelvic Health and require a preoperative visit will be identified and screened against inclusion and exclusion criteria. If patients meet the requirements for the study, they will be invited to participate in the study. The patients who do not meet inclusion criteria will be documented. Patients who decline to participate will be documented and reason will be noted. Participants will be consented for enrollment into the study by physicians, fellow physicians, and/or the research team prior to surgery. Participants will be randomized to one of the two counseling groups at the time of verbal consent.

PROVIDER AND CLINICAL STAFF TRAINING

To ensure consistent scheduling and counseling, the principal investigator will provide in-service education to all participating providers and clinical staff who will be

scheduling and performing preoperative visits. All clinical staff, including nurses, schedulers, and physicians, will receive in-service training about the study protocol and guidelines.

INCLUSION CRITERIA

1. Females age 18 and greater
2. Visit location in North Carolina (or South Carolina during COVID)
3. Planning to undergo pelvic surgery at Mercy Hospital, One Day Surgery Center, or CMC Main Hospital.
4. Scheduled for enhanced recovery perioperative protocol
5. Require a preoperative visit
6. Access to internet and a virtual visit capable device
7. Telephone access

EXCLUSION CRITERIA

1. Non-English speaking
2. Inability to provide consent/decisionally impaired
3. Auditory impairment
4. Required preoperative in-office procedure such as endometrial biopsy

STUDY WITHDRAWAL

Participants may withdraw from the study at any point in time. Documentation of the reason for withdrawal will be captured in the data collection forms. There will be no risk to participants that choose to withdraw from the study.

PREOPERATIVE PERIOD

All consecutive patients planning to undergo pelvic surgery who require a preoperative visit will be identified, screened, and approached for participation in the study. Participants who do not meet the inclusion and exclusion criteria will be considered screen failures. Screen failures will be captured and the cause for screen failure will be documented.

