Verbal consent will be obtained and accurate email address will be confirmed. Eligible subjects will be randomized using a computer-generated randomization scheme with patients assigned in a 1:1 ratio to either:

Study Group: Telemedicine preoperative counseling with an FPMRS fellow

Control Group: Standard in-office preoperative counseling with an FPMRS fellow

The allocation sequence will be in numerical, sealed, opaque envelopes. An envelope will be retrieved at the time of consent. The surgical scheduler will schedule the patient for their allocated preoperative visit.

Prior to their preoperative visit, participants will be emailed copies of the office ERAS informational booklet and International Urogynecology Association (IUGA) patient information handouts pertinent to their surgery. The preoperative visit at Women's Center for Pelvic Health is a counseling visit to review informed consent. Preoperative medical evaluation is accomplished through the Carolinas Hospitalist Group preoperative clinic or with the patient's primary care provider. Patients who require preoperative medical clearance will be scheduled for a preoperative visit with the Carolinas Hospitalist Group or their primary care provider in addition to their preoperative visit with the Women's Center for Pelvic Health. These visits will be documented in the total office visit data collection.

Women in the Telemedicine group will check in for their preoperative visit via an Atrium Information Systems (IS) approved virtual communication platform at the scheduled date and time. They will undergo preoperative counseling following a standardized checklist format. After telemedicine counseling has concluded, participants will be emailed a REDCap survey link to complete a survey regarding their preparation for surgery. (See Figure 2) If a participant has not completed the survey by the next business day, an email reminder will be sent to their email address on file. If they have not completed the survey within 2 business days, they will be contacted by phone for reminder or survey will be obtained in the preoperative area on day of surgery. If a participant in the Telemedicine group ultimately elects to have an in-office preoperative visit, they will be scheduled for in-office visit and analyzed as intention-to-treat.

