Women in the In-office group will present to WCPH for preoperative in-person counseling following a standardized checklist format. After in-office counseling has concluded, participants will be asked to complete a survey regarding preparation for surgery via a REDCap survey link on an Atrium IS approved iPad prior to leaving the office. (See Figure 2) If for any reason the patient did not complete the survey prior to leaving the office, the survey will be emailed to them in similar fashion as the telemedicine group.

PERIOPERATIVE PERIOD

Participants will present to Mercy Hospital, One Day Surgery Center, or CMC Main Hospital for their scheduled surgery. All participants will receive routine care according to the gynecologic enhanced recovery perioperative protocol. The gynecologic enhanced recovery perioperative protocol is a multimodal perioperative care pathway designed to achieve early recovery after surgery by maintaining preoperative organ function and reducing the physical stress of surgery on the body. This protocol includes many components including allowing patients to drink clear liquids up to 3 hours prior to their surgery, maintaining euvoemia intraoperatively, and early return to normal diet and activity after surgery. All patients undergoing pelvic reconstructive surgery are

scheduled for the enhanced recovery protocol, except for women having only minor procedures such as mid-urethral sling placement or cystoscopy.

POSTOPERATIVE PERIOD

All participants will undergo routine postoperative care. They will be scheduled for an in-office or virtual postoperative visit, on average 1-2 weeks after surgery and then an in-office visit at 6 weeks after surgery per our office standard practice. Following their 2-week postoperative visit, women will be asked to complete the preoperative subsection of the Surgical-CAHPS survey to evaluate patient satisfaction. This will be given to all patients in paper format prior to leaving the office or emailed to them via REDCap survey link. If a patient does not present to their 2-week postoperative appointment, they will be emailed a copy of the preoperative subsection of the S-CAHPS and this will be automatically uploaded into REDCap when submitted by the participant.

Following the 6 week postoperative visit, secondary data will then be extracted from the EMR via manual chart view.

RANDOMIZATION

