An Atrium Health biostatistician will generate a randomization sequence using SAS Enterprise Guide 6.1. A permuted block randomization scheme will be used to assign patients in a 1:1 ratio to Telemedicine visit or In-office visit.

The study will not be blinded.

DATA COLLECTION AND MANAGEMENT

Data Collection Schedule

Case report forms will be developed by the investigators. Data will be collected prospectively per the schedule in Table 1. All study data will be recorded by research staff and securely maintained at the Mercy study site. The data flow will consist of paper data collection for eligibility assessment, baseline data, randomization, intervention group, primary and secondary outcomes, and protocol deviations.

Data will be entered by study staff into REDCap database that will be stored on a secure server at Atrium Health. Web-based survey responses will be linked to REDCap for automatic entry following participant submission of surveys. REDCap (Research Electronic Data Capture) is a secure, web-based application designed to support data capture for research studies providing: 1) an intuitive interface for validated data entry; 2) audit trails for tracking data manipulation and export procedures; 3) automated export procedures for seamless data downloads to common statistical packages; and 4) procedures for importing data from external sources (13).

Each patient will have a unique identification number to which only the principal and sub-investigators will have access. The data collection spreadsheet will not contain any patient identifiers and will be password protected. The master list that links the patients and their study information will be stored separately on a password protected hard drive. A back up copy of the file will be stored on a password protected hospital network drive. All hard copies of study data will be stored in a locked cabinet in the office of the research nurse, which will also be locked.

Table 1. Data Collection Schedule

	Prior to Preoperative visit	Preoperative visit	Period between Preop visit and surgery	Surgery	2 week postop visit	6 week postop visit
Informed consent	X					
Randomization	X					
Travel distance	X					
Internet Access/Usage	X	X				
Other Demographics*	X	X				
Patient Preparedness		X				
Patient Satisfaction					X	
Office visits		X	X		X	X
Cost metrics						X

*Other demographic data includes: Age, Race, Education level, Health literacy score, and number of prior surgeries.

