If you want to know more about this study, please call [name] at [contact] or email at [contact]

Survey Instructions

Answer each question by clicking the box to the left of your answer. When you have selected your desired response, please click “Next”.

- 1 Yes
2 No

1. I know about the *Alternatives* to the planned surgery.

- 1 Strongly agree
- 2 Agree
- 3 Somewhat agree
- 4 Somewhat disagree
- 5 Disagree
- 6 Strongly disagree

2. I understand the *Purpose* of the planned surgery (what this surgery can accomplish).

- 1 Strongly agree
- 2 Agree
- 3 Somewhat agree
- 4 Somewhat disagree
- 5 Disagree
- 6 Strongly disagree

3. I understand the *Benefits* of the planned surgery (how this surgery should help me).

- 1 Strongly agree
- 2 Agree
- 3 Somewhat agree
- 4 Somewhat disagree
- 5 Disagree
- 6 Strongly disagree

4. I understand the *Risks* of the planned surgery (what are the chances of something not going the way my doctor and I want it to go?).

- 1 Strongly agree
- 2 Agree
- 3 Somewhat agree
- 4 Somewhat disagree
- 5 Disagree
- 6 Strongly disagree

5. I understand the *Complications* of the planned surgery (what problems can come from this surgery?).

- 1 Strongly agree
- 2 Agree
- 3 Somewhat agree
- 4 Somewhat disagree
- 5 Disagree
- 6 Strongly disagree

6. I feel prepared about *what to expect after surgery while I am in the hospital.*

- 1 Strongly agree
- 2 Agree
- 3 Somewhat agree
- 4 Somewhat disagree
- 5 Disagree
- 6 Strongly disagree

7. I feel prepared about *what to expect after surgery when I am at home.*

- 1 Strongly agree
- 2 Agree
- 3 Somewhat agree
- 4 Somewhat disagree
- 5 Disagree
- 6 Strongly disagree

8. I feel prepared to cope with a *catheter* after the surgery while I am at the hospital.

- 1 Strongly agree
- 2 Agree
- 3 Somewhat agree
- 4 Somewhat disagree
- 5 Disagree
- 6 Strongly disagree

9. I feel prepared to cope with a *catheter* after the surgery when I am at home.

- 1 Strongly agree
- 2 Agree
- 3 Somewhat agree
- 4 Somewhat disagree
- 5 Disagree
- 6 Strongly disagree

10. My doctors and nurses have spent enough time preparing me for my upcoming surgery.

- 1 Strongly agree
- 2 Agree
- 3 Somewhat agree
- 4 Somewhat disagree
- 5 Disagree
- 6 Strongly disagree

11. Overall, I feel prepared for my upcoming surgery.

- 1 Strongly agree
- 2 Agree
- 3 Somewhat agree
- 4 Somewhat disagree
- 5 Disagree
- 6 Strongly disagree

Think about the type of preoperative visit you had prior to your surgery.

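### The primary preparedness survey is by default answered on a clinic iPad in one arm and remotely from an emailed link in the other, so any effect of setting or delay counts as an effect of visit type

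*Combined protocol and SAP*

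**What the plan says.** The Preoperative Period section sets a separate default route for each arm.

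- **In-office:** once counselling ends, participants are asked to complete the survey "via a REDCap survey link on an Atrium IS approved iPad prior to leaving the office". If that does not happen, "the survey will be emailed to them in similar fashion as the telemedicine group".
- **Telemedicine:** "After telemedicine counseling has concluded, participants will be emailed a REDCap survey link to complete a survey regarding their preparation for surgery". An email reminder follows after one business day. After two, there is a phone reminder, or the survey is collected before the operation on the day itself.

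Three provisions apply to everyone. Eligibility requires "Access to internet and a virtual visit capable device". At enrolment, "Verbal consent will be obtained and accurate email address will be confirmed". Under Data Collection and Management, "Web-based survey responses will be linked to REDCap for automatic entry following participant submission of surveys".

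The Randomization section states: "The study will not be blinded". The primary outcome is the sum of 11 self-rated six-category items (Outcome Measures; Figure 2). Item 10 is a rating of the staff: "My doctors and nurses have spent enough time preparing me for my upcoming surgery". Statistical Methods compares the summary scores between groups. The plan contains no adjustment or sensitivity analysis for where or when the survey was answered, and no stated recording of either.

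**The concern.** The survey is a research measurement and not part of either visit, yet its default setting follows the allocation. Randomisation balances patients; it does not remove a measurement difference that is applied by arm.

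An in-office patient normally answers at once, on the premises of the staff who counselled her. A telemedicine patient answers elsewhere, at once or some days later. With open allocation and a self-rated score, either difference could move the answers.

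The stakes depend on direction. If patients answer more favourably in the clinic, telemedicine looks worse and power is lost. If a later answer is more favourable, for example after more reading, telemedicine looks better and a false non-inferiority claim becomes more likely. Because route nearly coincides with arm, and the few patients who change route do so by choice or circumstance, adjustment afterwards cannot reliably separate the two effects.

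**Working it through.** **Inputs (Sample Size Calculation; Statistical Methods).** Margin 9, SD 15, 45 evaluable per arm, power 0.80, one-sided alpha 0.025. Statistical Methods bases the decision on a one-sided 95% limit, which is alpha 0.05. The two sections disagree on alpha, which is a separate matter, so both levels are shown.

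**Step 1. Reproduce the plan's figure.** SE = 15 × √(2/45) = 3.162, with 88 degrees of freedom. The non-centrality at a true difference of zero is 9/3.162 = 2.846. The non-central t gives power 0.804 at 45 per arm and 0.795 at 44, so 45 is reproduced. At alpha 0.05, power with 45 per arm is 0.881.

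**Step 2. Add an assumed shift b from setting or delay.** The documents give no size for it, so b is purely illustrative.

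- Shift against telemedicine, true difference zero: the distance to the margin becomes 9 − b, and the non-centrality (9 − b)/3.162, which is 2.530 for b = 1 and 2.214 for b = 2.
- Shift in favour of telemedicine, true difference exactly 9: the apparent difference is 9 − b, so the non-centrality for the false claim is b/3.162.

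| Assumed shift b (points) | Power, alpha 0.025 | Power, alpha 0.05 | False non-inferiority, alpha 0.025 | False non-inferiority, alpha 0.05 |
|---|---|---|---|---|
| 0 | 0.80 | 0.88 | 2.5% | 5.0% |
| 1 | 0.71 | 0.81 | 5.0% | 9.2% |
| 2 | 0.59 | 0.71 | 9.1% | 15.5% |

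The power columns take the shift as adverse to telemedicine; the false-claim columns take it as favourable.

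**Step 3. Scale of a shift.** Spread evenly over 11 items, 1 point is 1/11 = 0.09 of a category per item. If it came from item 10 alone, the average answer to that item would have to move by a whole category.

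**Step 4. Unequal response.** If a fraction r responds and non-responders would score D points worse, the completers' mean is better than the full-arm mean by (1 − r) × D. With assumed final response of 90% on the iPad default and 70% on the email default, and D = 5, telemedicine would look better by (0.30 − 0.10) × 5 = 1.0 point. For D = 3 or 10 the figure is 0.6 or 2.0.

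**Step 5. Cost of moving in-office patients to email.** At alpha 0.025, with 45 telemedicine completers and 41 or 36 in-office completers (4 or 9 lost), SE = 15 × √(1/45 + 1/41) = 3.238 or 15 × √(1/45 + 1/36) = 3.354. Power is 0.784 or 0.755, a loss of 0.02 or 0.05 from 0.804.

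**The case against.** The strongest reply is that little actually differs. Both arms use the same self-completed electronic form, prompted when counselling ends, and the survey promises confidentiality. In-office non-completers move to the telemedicine route. This stands, and it confines the point to the first place of completion and any delay. It does not remove the point, because most in-office patients should never reach the fallback.

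A reader might infer that the email route will lose more of the less prepared telemedicine patients and so produce a false non-inferiority claim. The documents do not support that as a likely outcome. They give no response rate by route, the 30% dropout allowance is not split by arm, and anyone who comes to surgery can still be reached by phone or on the day. A final gap of 20 percentage points fits poorly with those steps. Such a bias is possible but should be small, and the conclusion does not rest on step 4.

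A reader might also lean on item 10. It is one item of 11, so the shifts in step 2 would need some effect on the items about the patient's own understanding and coping as well. None is documented.

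Quoting only the alpha 0.025 figures would overstate the power loss: under the one-sided 95% rule a 1-point adverse shift leaves power at 0.81, still above the planned 0.80. The same rule makes the false-claim figures higher, so neither set should be shown alone.

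Finally, the fix has its own asymmetry. In-office patients travel home before answering, and near-certain completion in that arm is given up. If response fell to 70% in both arms, 59 × 0.70 ≈ 41 completers per arm would give power of 0.77 at alpha 0.025. This is a fair cost, but the phone and day-of-surgery steps limit it, and it is a modest loss of precision in place of a possible bias that analysis cannot repair.

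**Conclusion.** The point holds in this limited form: the default setting, and possibly the timing, of the primary measurement follows the arm, and the planned comparison cannot tell its effect from that of visit type. That much follows from the text. Whether any such effect exists, in which direction and of what size, is unknown.

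The illustrative figures rest on a uniform shift of 1 or 2 points across the affected arm, SD 15, and 45 completers per arm; the false-claim figures also require the true difference to equal the margin. They show that a shift that is small beside the margin of 9 would matter. They do not show that one will occur, and the documents do not support saying that the trial is biased towards or against telemedicine. The change is worth making because it is cheap and has to be made in the design. Confidence is medium.

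**What to change.** Amend the Preoperative Period section so that both arms follow one procedure:

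- Email the same REDCap link to every participant at the end of the visit, in place of on-site iPad completion as the in-office default.
- Use the same reminder schedule in both arms and one stated completion window ending before surgery, with the existing phone and day-of-surgery collection as the common backstop.
- Keep every survey completed before surgery in the primary intention-to-treat analysis.
- Record route and completion date for each survey and report both by arm. Treat any analysis by route or timing as supportive only, because both arise after randomisation and may still differ by arm.

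The amendment is short: internet access, confirmed email addresses, REDCap and the reminder workflow are already in place for all participants. No sample-size figure changes. The downside is that some in-office surveys may be lost or completed later, at a power cost of about 0.02 to 0.05 if 4 to 9 of 45 are lost. The common window limits the delay.

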STUDY TITLE

In Office versus Telemedicine Preoperative Visit: A Randomized Controlled Trial

PRINCIPAL INVESTIGATOR

[name]
[name]
[name]
[contact]

CO-INVESTIGATORS

[name]
[name]
[name]
[contact]

[name]
[name]
[name]
[contact]

[name]
[name]
[name]

STUDY OBJECTIVES

PRIMARY OBJECTIVE

To determine whether preoperative telemedicine appointments are non-inferior to in-office visits based on patient preoperative preparedness in women undergoing pelvic surgery as measured by a preoperative preparedness survey.

SECONDARY OBJECTIVES

1. Evaluate patient satisfaction using the S-CAHPS survey
2. Calculate the duration of visit for patient (minutes)
3. Calculate the duration of visit for provider (minutes)
4. Estimate round trip travel distance from patient home to clinic (miles)
5. Evaluate the number of office contacts from date of preoperative counseling to 6 weeks postoperatively.
 - a. Patient initiated calls
 - b. Nurse initiated calls

- c. Scheduled office visits
- d. Add on office visits
6. Evaluate canceled, no-show, and late visits
7. Calculate value proposition metrics for Atrium Health System

HYPOTHESIS

Telemedicine visits will be non-inferior to in-office visits in readying patients for surgery based on a preoperative preparedness survey. Additionally, we hypothesize that women will be equally satisfied with telemedicine preoperative visits as compared to in-office preoperative visits.

BACKGROUND

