Source of records to be reviewed

- Canopy EMR (electronic medical record)
- Preoperative Preparedness Survey
- S-CAHPS survey

Confidentiality of data

Electronic data will be stored to safe-guard confidentiality using a password protected computer. Principal investigator, Co-Investigator, Research Coordinator nurse, and Statisticians will have access to harvested patient data. Harvested patient data will be stored until final statistical analysis completed and manuscript accepted and published.

OUTCOME MEASURES

Primary Outcome Measure

- a. **Patient Preoperative Preparedness:** Participants will complete a Preoperative Preparedness Survey following the preoperative visit. This will be graded on a 6-point Likert scale with responses ranging from “Strongly

Agree” to “Strongly Disagree”. The summary score of 11 items will be calculated as the measurement of primary outcome. See Figure 2.

Secondary Outcome Measure

- a. **Patient Satisfaction:** Patients will complete the preoperative portion of the Consumer Assessment of Healthcare Providers and Systems Surgical Care Survey (S-CAHPS) following the 2-week postoperative visit. S-CAHPS is a validated standardized questionnaire for adults developed by the American College of Surgeons (ACS) and other surgical specialty societies to assess patients’ experiences before, during, and after surgery. The preoperative portion of this survey includes questions regarding Patient Satisfaction, Physician Communication, and Shared Decision Making. See Figure 3.
- b. **Duration of visit:** Each preoperative visit will be timed to evaluate patient and provider visit duration. Timing will begin for the Telemedicine group upon connection to the virtual waiting room and will conclude after all counseling is completed and the virtual visit is disconnected. The duration of virtual visit counseling time with the provider will also be calculated. Timing for the in-office group will begin at time of patient check-in at the front desk and will conclude with patient check-out.
- c. **Miles patient traveled:** Round trip travel distance from patient’s home address to office will be evaluated via a HIPPA compliant map-based search engine for each participant.

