- d. **Office contacts:** The total number and type of office contact between the preoperative visit and the 6-week postoperative visit will be collected via manual chart review. Type of office contact visits include patient-initiated calls, nurse-initiated calls, scheduled office visits, and add-on office visits.
- e. **Canceled, No-show, and late visits:** If patients call to cancel their appointment this will be considered a canceled preoperative visit. Rescheduled appointment will be noted. Patients who arrive to their visit later than 10 minutes will be considered late for each group. If patients do not present for their visit, it will be considered a No-show appointment.
- f. **Calculated value proposition metrics:** The length of visit will be compared between groups. Office schedules will be analyzed and will determine the percentages of new patient visits and preoperative visits. If preoperative visits are replaced with new patient visits over a month, based on institutional data, anticipated new operative cases and projected revenue impact on the health care system will be determined. Costs of video based virtual visit platform will also be calculated.

STATISTICAL CONSIDERATIONS

Statistical Methods

The primary analysis will compare summary scores of preparedness between both study groups. Non-inferiority of virtual visit compared with in-person visit

would be claimed if the upper limit of the one-sided 95% confidence interval for the mean differences of scores between two groups will not exceed the pre-specified margin of 9 points. Descriptive statistics will be calculated to assess level of preparedness for each question. Secondary outcomes, demographics, and other baseline variables will be compared between the two groups using the Chi squared test or Fisher's exact test for categorical data, Student's t test for normally distributed data, and the Wilcoxon rank sum test for ordinal data or continuous data that are not normally distributed.

Sample Size Calculation

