12. Please select the type of visit you had:

- ¹ In-office visit
² Virtual visit

13. How satisfied are you with the visit that you had before your surgery?

- ¹ Very satisfied
² Satisfied
³ Neither satisfied or dissatisfied
⁴ Not satisfied
⁵ Very dissatisfied

14. How would you rate the level of convenience of the visit (virtual or in-person)?

- ¹ Very convenient
² Convenient
³ Neither convenient or inconvenient
⁴ Not convenient
⁵ Very inconvenient

15. If you need to have surgery in the future, would you like to have this type of visit again?

- ¹ Yes
² No
³ Not sure

16. Would you recommend the type of visit you had to a friend?

- ¹ Yes
² No
³ Not sure

17. If in the future our clinic offered the option to have a preoperative visit using virtual visit technology or an in-person clinic visit, which would you prefer?

- 1 Virtual visit
- 2 In-person clinic visit
- 3 No preference

18. What types of technology have you used in the past to access health care services or personal health information? Select all that apply:

- 1 Video conferencing (virtual visit)
- 2 Email
- 3 Text messaging
- 4 Patient Portal (e.g. My Carolinas)
- 5 Mobile health (accessing health services or personal health data via mobile devices)
- 6 Other: _____
- 7 None

The following questions will help us determine comfort level with health information.

19. How often do you have someone (like a family member, friend, hospital/clinic worker, or caregiver) help you read hospital materials?

- 1 None of the time
- 2 A little of the time
- 3 Some of the time
- 4 Most of the time
- 5 All of the time

20. How often do you have problems learning about your medical condition because of difficulty understanding written information?

- 1 None of the time
- 2 A little of the time
- 3 Some of the time
- 4 Most of the time
- 5 All of the time

21. How confident are you filling out forms by yourself?

- 1 Extremely
- 2 Quite a bit
- 3 Somewhat
- 4 A little bit
- 5 Not at all

Figure 3. Postoperative visit survey

Your Privacy is Protected. All information that would let someone identify you or your family will be kept private. The Women’s Center for Pelvic Health will not share your personal information with anyone. Your responses to this survey are also completely **confidential**.

Your Participation is Voluntary. You may choose to answer this survey or not. If you choose not to, this will not affect the health care you get.

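### The office-contact count leaves out patients' written messages, so a lower count with telemedicine could reflect the channel used and not the need for contact

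*Combined protocol and SAP*

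**What the plan says.** Secondary Objectives, item 5, sets the aim: "Evaluate the number of office contacts from date of preoperative counseling to 6 weeks postoperatively". Its sub-items a to d name two kinds of telephone call and two kinds of office visit. Outcome Measures, Secondary Outcome Measure d, repeats the aim as "The total number and type of office contact between the preoperative visit and the 6-week postoperative visit will be collected via manual chart review" and then gives the types: "Type of office contact visits include patient-initiated calls, nurse-initiated calls, scheduled office visits, and add-on office visits". Neither place names a portal message, an email or a text, and neither has a residual category.

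The written channels do appear elsewhere. Item 18 of the Preoperative Preparedness Survey (Figure 2) asks which technologies the respondent has used for health care or health information. Its answers include email, text messaging and "Patient Portal (e.g. My Carolinas"). Inclusion Criteria, item 6, requires internet access and a device able to run a virtual visit. Under Preoperative Period, an email address is confirmed at consent and used to send the booklet, the handouts and, where needed, the survey link.

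**The concern.** The outcome promises a total number of contacts, but as listed it is a total of calls and visits only. A woman who writes to the office with a question has contacted it just as one who telephones has, yet only the second is counted.

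This matters more here than in most trials because the randomised factor is itself a mode of communication. One arm is counselled on a virtual platform and the other in the clinic. It is plausible, though not shown, that women in the first arm would also send later questions electronically more often. The telemedicine arm would then show fewer patient calls and a lower total, and this could be reported as a lighter load on the office or as a sign of adequate counselling when the number of questions was the same. The study is unblinded, so it should not be left to the abstractor to decide case by case whether a message counts.

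**Working it through.** **Step 1: is the omission made good elsewhere?**

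- Table 1 (Data Collection Schedule) has one row that bears on contacts, "Office visits". It has no row for calls or messages.
- Preoperative Period widens the visit data to medical clearance visits: "These visits will be documented in the total office visit data collection". It adds nothing on written contact.
- Postoperative Period allows a virtual visit at 1-2 weeks: "They will be scheduled for an in-office or virtual postoperative visit". The four types do not say where such a visit belongs, which is a second sign that the list was not written to cover every route.
- Statistical Methods gives general two-group tests for secondary outcomes and no rule for contacts outside the four types.

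Nothing restores written contacts to the count.

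**Step 2: size.** The plan states no expected contact count, standard deviation, margin or power for this outcome, so there is no plan figure to reproduce. All inputs below are assumptions.

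- m = true mean number of contacts per patient, all channels, equal in both arms. Assumed 3, with a range of 2 to 4.
- sT and sC = share of contacts left uncounted because they are written, in the telemedicine and in-office arms.

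Counted means are m(1 − sT) and m(1 − sC). The observed difference, telemedicine minus in-office, is m(1 − sT) − m(1 − sC) = −m(sT − sC). The ratio (1 − sT)/(1 − sC) does not depend on m.

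| sC (in-office) | sT (telemedicine) | Counted means at m = 3 (in-office, telemedicine) | Difference at m = 3 | Difference at m = 2 and m = 4 | Ratio |
|---|---|---|---|---|---|
| 20% | 20% | 2.4, 2.4 | 0 | 0, 0 | 1.000 |
| 20% | 30% | 2.4, 2.1 | −0.3 | −0.2, −0.4 | 0.7/0.8 = 0.875 |
| 10% | 30% | 2.7, 2.1 | −0.6 | −0.4, −0.8 | 0.7/0.9 = 0.778 |
| 20% | 40% | 2.4, 1.8 | −0.6 | −0.4, −0.8 | 0.6/0.8 = 0.750 |
| 30% | 20% | 2.1, 2.4 | +0.3 | +0.2, +0.4 | 0.8/0.7 = 1.143 |

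The true difference is zero in every row. Equal shares lower both means and create no difference. Unequal shares create one, and its sign follows whichever arm writes more. The last row shows that the bias could also run against telemedicine.

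**The case against.** Several points on the other side are sound.

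- *The list may be open.* Outcome d introduces the four types with the verb include, which need not be exhaustive. But objective 5 gives the same four with no catch-all, and an open list in an unblinded study still needs a written rule. The open reading changes the reason for the fix, not the need for it.
- *The survey does not show current use.* Item 18 asks about past use and offers none as an answer. Email is described only for study materials and survey links. This stands: the documents show that the channels are recognised, not that this office receives clinical questions through them.
- *The arms differ in one visit.* Both need internet access, both receive the same emailed materials, and postoperative visits may be virtual in either arm. Channel shares may therefore be similar, in which case no difference is created. A message answered by telephone may also be caught as a nurse call. Both points stand and limit the likely size.
- *It is a minor outcome.* It is one of seven secondary objectives, with no hypothesis, margin or power attached. This stands too.

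A reader might go further and infer three things that the documents do not support.

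- *That this is the only measure taken after counselling.* S-CAHPS is collected after the 2-week visit, and adverse events are logged and reviewed by an independent safety monitor.
- *That leaving out emergency department visits and readmissions is an error that reverses the result for poorly prepared patients.* These are not office contacts, so omitting them fits the outcome as named, and no figure in the documents bears on a reversal.
- *That a patient who only writes would score zero on unplanned contacts.* The protocol defines no such score.

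**Conclusion.** The concern holds for written contacts. As listed, the four types leave patient-initiated portal messages, emails and texts out of a quantity described as a total, and no other section puts them back. A lower count with telemedicine could then not be told apart from a change of channel.

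Whether there is any bias in the comparison depends on channel shares that the documents do not give. With no true difference, it is zero if the shares are equal. At an assumed mean of 3 it is −0.3 contacts per patient for 30% against 20%, and −0.6 for 30% against 10% or 40% against 20%. It changes sign if the in-office arm writes more. These figures illustrate the mechanism and do not estimate the bias. The point bears on the reading of one secondary outcome. The preparedness comparison and its non-inferiority conclusion do not depend on it.

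**What to change.** In Secondary Objectives item 5 and Secondary Outcome Measure d:

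1. Keep the four existing categories, including nurse-initiated calls.
2. Add a fifth, patient-initiated written contacts (portal, email, text), with a stated rule for counting a thread of several messages.
3. State that the five-category list is closed, and say in which category a virtual postoperative visit is counted.
4. Report each type and the total by arm, so that a shift between channels is visible.

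Optionally, emergency department visits and readmissions found in the same chart may be reported descriptively by arm, kept apart from the office-contact total. This would be an added outcome and not a correction.

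The cost is modest abstraction time in a manual chart review already planned after the 6-week visit. The record source listed is "Canopy EMR (electronic medical record"), so emails and texts that were never filed there will still be missed. The report should state that limit.
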